3.4 Subject Selection and Enrollment Considerations

RUTGERS APPROVED

Protocol Version 1.0 - 04/21/15

IRB ID: Pro20150001531

Approval Date: 4/30/2015

Expiration Date:

Add protocol title
PI name

All comers to the antenatal clinic and labor and delivery unit will receive the same educational information. Those women who are not English or Spanish speaking will not be provided with the written educational material and information letter.

3.5.1 Inclusion Criteria

1. Postpartum women ages 18 and older
2. Patients who speak and read English or Spanish
3. Patients who received our informational pamphlet while pregnant or in labor
4. Patients who are able to consent and make medical decisions
5. Patients undergoing labor or trial of labor after cesarean delivery
6. Patients who undergo cesarean delivery after trial of labor

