Title of Project: The effects of antenatal and perinatal education of labor analgesia options on maternal anxiety, labor analgesia and maternal satisfaction

Principal Investigator: [name]

Funding Source(s): NJMS Anesthesiology Department

1. Purpose/Specific Aims

The specific aim of the study is to determine if education in the antenatal period and repeated upon arrival to Labor and Delivery regarding labor analgesia options is useful in reducing maternal anxiety and improving patient satisfaction.

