1.2 Hypotheses

The hypothesis is that providing written material regarding labor analgesia options will improve maternal satisfaction and lessen anxiety in regard to labor.

2. Background and Significance

Background

Many analgesic options exist for laboring parturients, but labor may not be the best time to start informing patients of their options. Many patients begin the labor process with a plan in place for their analgesia. Unfortunately, internet resources regarding labor analgesia that are available to the lay parturient are poor and often lead to misconceptions about the options and their risks. A significant number of patients refuse neuraxial analgesia based on misunderstandings, concerns about the procedure, or a lack of faith in the provider. Some women want a “natural childbirth” and/or control over their labor experience. Forty-seven percent of minority women feel inadequately educated about anesthesia, are less likely to trust physicians, and are less likely to receive epidurals. However, greater than 10% of obese women changed their preference toward epidural analgesia following antenatal consultation. Also, 50% of patients planning for analgesia-free labor request neuraxial analgesia after experiencing labor pain.³

Additionally, the question exists as to the quality of informed consent from a patient undergoing contraction pain and possible sedation from analgesic medications. The

RUTGERS APPROVED

THE STATE UNIVERSITY OF NEW JERSEY

Protocol Version: 20150001/531

Approval Date: 4/30/2015

Expiration Date:

Add protocol title
PI name

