consensus is that parturients can provide informed consent. However, the process of informed consent for labor analgesia is not standardized; the options and risks presented to patients are dependent upon the individual practitioner obtaining the consent. Regarding epidurals, patients want to be informed of all risks and complications associated with the procedure.⁵ The patient's recall of the risks and benefits of the epidural procedure improved by 50% with written material in addition to verbal discussion, and recall improved by more than a factor of five when consent during labor was preceded by antenatal education. Parturients want a "pre-operative" visit with an anesthesiologist and have a strong desire for pre-labor education of anesthesia/analgesia options. Early antenatal education allows for unpressured time to teach, relieves anxiety, develops rapport, and provides opportunities for additional testing, if needed.³ Finally, the timing of epidural placement has not been shown to change outcomes, but when initiated late in the labor process, often other analgesia modalities were used that confounded the analysis of outcomes. Therefore, earlier request, which may come with prior knowledge and avoidance of misconceptions, and earlier placement of epidurals may lead to fewer analgesic interventions in the parturient and possibly less morbidity for the patient and fetus.

3. Research Design and Methods

This is a prospective study where written educational material will be dispensed to women when they visit the antenatal clinic during the course of their gestational visits. The material will again be provided upon admission to Labor and Delivery and a conversation will take place with the anesthesia care provider regarding the options for analgesia.

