3.1. Duration of Study

The study will commence upon receipt of the written educational material in the subject's preferred language. The material will provide a second time upon arrival to the Labor and Delivery Suite and at that time a discussion will be held with the anesthesia care provider regarding the options and their risks and benefits for analgesia and anesthesia for labor and delivery (15-20 minutes). The study will end following delivery when the subject completes the survey on the post-partum unit on F Green. The survey is expected to take 10-15 minutes.

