4.2 Dependent Variables or Outcome Measures

Study instruments are as follows:

Labor Pain Control Pamphlet –English and Spanish

We will provide information of available labor analgesia options (epidural, combined spinal/epidural, spinal, remifentanyl patient-controlled analgesia, and intravenous opioids) to expecting mothers. Using a pamphlet written in English or Spanish disseminated to pregnant women in clinic or in the labor and delivery unit, the procedures and their risks and benefits will be explained in simple terms.

Questionnaire- English and Spanish

After delivery, patients will be asked to complete a questionnaire addressing their thoughts about the pamphlets and their overall satisfaction with their labor analgesia. Our analysis will focus on the utility and effect of education materials on maternal informed consent for labor analgesia, on maternal choice of analgesia modality, and on maternal anxiety regarding their labor analgesia plan.

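### The specific aim is antenatal education repeated on arrival, but inclusion criterion 3 also admits women first given the pamphlet in labor, and all count toward one set of 100 surveys

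*Protocol*

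**What the plan says.** **Two contacts.** The specific aim (Section 1) concerns "education in the antenatal period and repeated upon arrival to Labor and Delivery". Section 3 has the material handed out at antenatal visits and adds: "The material will again be provided upon admission to Labor and Delivery". Section 3.1 repeats this: "The material will provide a second time upon arrival to the Labor and Delivery Suite". A discussion with the anesthesia provider is planned at the same point.

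**One contact is enough.** Inclusion criterion 3 (Section 3.5.1) reads: "Patients who received our informational pamphlet while pregnant or in labor". Section 4.2 describes the pamphlet as "disseminated to pregnant women in clinic or in the labor and delivery unit".

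**No timing.** The hypothesis (Section 1.2), the objectives (Section 1.1) and the sample size text (Section 3.3) speak of written or educational material without saying when it is given. Section 3.4 states: "All comers to the antenatal clinic and labor and delivery unit will receive the same educational information".

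**Delivery and data.** Section 3.5.3 leaves the pamphlets visibly in the clinic waiting area and says the visiting faculty member is unlikely to meet every patient. Section 3.3 sets one target of 100 surveys. Section 4.1 lists no independent variable, and Section 3.6 marks chart review as not applicable. Under Section 5 the survey is anonymous with no link kept, results are means, standard deviations and percentages, and the tests of demographic data name no groups.

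**The concern.** The aim joins the two contacts with *and*; the entry criterion joins them with *or*. A woman who received the pamphlet only in labor missed the contact on which the protocol's rationale rests. Section 2 argues that "labor may not be the best time to start informing patients of their options" and that "Early antenatal education allows for unpressured time to teach, relieves anxiety, develops rapport". Anxiety is one of the study's outcomes.

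If timing of receipt is not captured, a result offered as the answer to the specific aim would mix women who had the antenatal contact with women who did not. With no linkage and no chart review, no later analysis could separate them. That is why this is a protocol matter and not only one for an analysis plan: an analysis plan can define groups only from recorded data.

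There is a second, separate point. Section 3.3 expects the surveys to help establish whether the written literature is effective in reducing anxiety and improving satisfaction. The planned education is pamphlet plus provider discussion, given to a single group with no comparator.

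**Working it through.** **1. The plan's own figure.** Section 3.3 gives 100 surveys with no error rate, power, effect size, standard deviation or expected percentage. The figure cannot be reproduced, and this point does not depend on it.

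**2. Who is eligible, and whom the aim describes.**

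| Pamphlet received | Criterion 3 | Hypothesis (1.2) | Specific aim (1) and design (3, 3.1) |
|---|---|---|---|
| Clinic and admission | eligible | fits | fits |
| Admission or labor only | eligible | fits | does not fit |
| Clinic only | eligible | fits | does not fit |

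Exclusion 7 (Section 3.5.2) removes late presenters only where an analgesic intervention was precluded, so other labor-only women remain.

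**3. Can timing be recovered?** Not by linkage (Section 5) and not from charts (Section 3.6). The questionnaire is the only route.

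**4. Illustration of size.** Let f be the labor-only share and d the difference in a percentage (for example, satisfied) between women with both contacts and labor-only women. Both are assumptions. Clinic-only women are left out for simplicity.

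Pooled % = (1 − f) × P(both) + f × P(labor only), so the shift from P(both) is f × d in size.

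The 95% half-width near 50% is 1.96 × √(0.25/n). At n = 100 it is 9.8 points (standard error 5.0).

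| f | Women with both contacts | Shift, d = 10 | Shift, d = 20 | Half-width, both-contacts group |
|---|---|---|---|---|
| 0.25 | 75 | 2.5 | 5 | 11.3 |
| 0.50 | 50 | 5.0 | 10 | 13.9 |
| 0.75 | 25 | 7.5 | 15 | 19.6 |

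At d = 20 the shift reaches 9.8 points at f = 9.8/20 = 0.49. At d = 0 it is zero.

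**5. Does separating always give a better estimate?** Compare root-mean-square error for the both-contacts percentage. Pooled: √(shift² + 5.0²). Subset: 100 × √(0.25/n).

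| f | Pooled, d = 10 | Pooled, d = 20 | Subset |
|---|---|---|---|
| 0.25 | √(6.25 + 25) = 5.6 | √(25 + 25) = 7.1 | 5.8 |
| 0.50 | √(25 + 25) = 7.1 | √(100 + 25) = 11.2 | 7.1 |
| 0.75 | √(56.25 + 25) = 9.0 | √(225 + 25) = 15.8 | 10.0 |

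At a 10-point difference pooling is as accurate or slightly better. At 20 points the subset is better throughout. So the case for separation is that the result should describe the group named in the aim; it is not a guaranteed gain in accuracy.

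**The case against.** **Labor-only entry looks deliberate.** The hypothesis, objectives and sample size text name no timing, Section 3.4 includes women coming to the labor unit, and criterion 3 and Section 4.2 agree with each other. This stands. Labor-only women are properly in the study; the mismatch is only with the specific aim and the design text.

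**The questionnaire may already ask.** It is not reproduced, Section 4.2 says it covers women's thoughts about the pamphlets, and reporting by exposure group is ordinary analysis-plan content. This also stands. A reader might infer that timing is not collected, but the document does not show that. What remains is that no other source exists, so the item has to be confirmed before surveys are handed out.

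**Sections 3.4 and 3.5.3 do not contradict each other.** A reader might take the promise to all comers as refuted by pamphlets left in a waiting room. But admission delivery can reach everyone, the pamphlets are to be clearly visible, and picking one up needs no faculty visit. Section 3.5.3 makes missed antenatal receipt plausible, no more.

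**Clinic-only women are not deviations.** Their experience departs from the planned second contact, which might tempt a reader to class them so, but criterion 3 expressly admits them.

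**The attribution point is a different issue, and Section 3.3 is hedged.** It is indeed separate from criterion 3. The hedge is thin, however: the text still presents 100 single-group surveys as the basis for deciding effectiveness.

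**Conclusion.** The point holds as a mismatch between the specific aim and design (antenatal contact plus repeat) and the entry criterion and Section 4.2 (either contact), with one set of 100 surveys and no separation stated in the protocol. It is worth correcting because the remedy is cheap and must come before data collection.

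The size of any bias is unknown. A reader might infer from the illustration that the pooled result will be materially wrong. The protocol does not support that: it gives neither the labor-only share nor an expected difference, and under the assumed 10-point difference pooling costs no accuracy.

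On Section 3.3, one group given pamphlet plus discussion, with no comparator, can describe women's reported views of the education as delivered. It cannot establish that the written literature is effective. The study is descriptive with or without the changes below.

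**What to change.** 1. Reconcile Sections 1, 3 and 3.1 with criterion 3 and Section 4.2, stating which exposure the specific aim concerns. Keep eligibility broad.
2. Confirm that both the English and the Spanish questionnaire record (a) receipt of the pamphlet before labor, on admission, or both, and (b) whether the provider discussion took place. Add tick-box items if they are absent.
3. Report the specific aim in women with both contacts. Show labor-only and clinic-only women as two further descriptive groups, not as deviations.
4. Reword Section 3.3 so that the surveys describe women's views of the education as delivered, without claiming to establish the effectiveness of the written literature.

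**Cost.** Protocol wording and at most two tick-box items per language; no extra patients. The group matching the aim will be smaller than 100 and its estimates less precise, as the half-widths above show for assumed sizes. Timing will rest on postpartum recall, and antenatal receipt is partly self-selected, so differences between the groups should not be read as effects of timing.

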3.5.2 Exclusion Criteria

1. Patients unable or unwilling to complete questionnaire
2. Patients unable to consent or make medical decisions
3. Patients less than 18 years of age
4. Patients unable to read and speak English or Spanish
5. Patients in whom any of the analgesic options were contraindicated
6. Patients with a history of an anxiety disorder
7. Patients with precipitous labor or late presentation that precluded an analgesic intervention
8. Patients with fetal distress that precluded an analgesic intervention
9. Patients planned for elective cesarean section.

3.5.3 Subject Recruitment

Education materials will be left in both languages in the waiting area of the obstetrical clinic. They will be placed in an area where they are clearly visible for the potential subjects. A member of the anesthesia faculty visits the clinic several times per month but it is not likely he will see each and every patient coming to the clinic.

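### Antenatal receipt of the pamphlet is partly voluntary pick-up, so the 100 surveys can mix antenatally educated and labor-only women in unknown, self-selected proportion

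*Protocol*

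**What the plan says.** The aim in Protocol Section 1 concerns education given antenatally and then repeated on arrival at Labor and Delivery. The sections that describe how women get the material differ:

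- Section 3 (Research Design and Methods): "written educational material will be dispensed to women when they visit the antenatal clinic during the course of their gestational visits". It continues: "The material will again be provided upon admission to Labor and Delivery", together with a conversation with the anesthesia care provider.
- Section 3.4: "All comers to the antenatal clinic and labor and delivery unit will receive the same educational information", apart from women who speak neither English nor Spanish.
- Section 3.5.3: "Education materials will be left in both languages in the waiting area of the obstetrical clinic", placed where they can easily be seen. An anesthesia faculty member attends the clinic several times a month, but "it is not likely he will see each and every patient coming to the clinic".
- Section 3.5.1, criterion 3, admits "Patients who received our informational pamphlet while pregnant or in labor". Section 4.2 likewise has the pamphlet "disseminated to pregnant women in clinic or in the labor and delivery unit".

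Section 3.3 sets a target of 100 completed surveys. Section 5 makes the survey anonymous with no link to identifiers, Section 3.6 rules out chart review, and Section 4.1 lists no independent variable.

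**The concern.** Sections 3 and 3.4 read as if every clinic patient is given the pamphlet before labor. Section 3.5.3 contains no step that achieves this. A woman may take the pamphlet, overlook it or leave it, and the only staff contact mentioned is admitted to be incomplete. Antenatal receipt is thus not assured and depends partly on her own choice.

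Antenatal timing is the study's rationale. The background in Section 2 credits education before labor with much better recall and with unpressured time to teach. If the surveyed women are an unknown blend of those educated in pregnancy and those first given the pamphlet in labor, a favorable rating does not show which component earned it. Any later split by exposure would compare women who chose to take the pamphlet with women who did not.

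**Working it through.** **Plan's own figure.** The 100 surveys are a target with no error rate, power, effect size or expected proportion behind them, so there is nothing to reproduce. The point is about delivery and attribution and does not dispute that number.

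**Step 1: who can be in the survey.** Read together, the sections allow three histories:

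| History | Permitted by | Matches the Section 1 aim? |
|---|---|---|
| Clinic and again on admission | 3, 3.1, 3.5.1 | Yes |
| Admission only | 3.5.3 with 3, 3.1, 3.5.1 | No, antenatal part absent |
| Clinic only (admission step missed) | 3.5.1, 4.2 | No, repeat absent |

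The protocol does not give the shares and names no record of them.

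**Step 2: what the blend does to attribution.** Illustration on assumed values: 75 of 100 respondents rate the pamphlet helpful and 50 of the 100 had it antenatally. If all 50 labor-only women rated it helpful, the antenatal count is 75 − 50 = 25, or 25/50 = 50%. If only 25 of them did, it is 75 − 25 = 50, or 50/50 = 100%. The same overall 75% fits any antenatal rating from 50% to 100% unless exposure is recorded.

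**Step 3: could pick-up bias the ratings?** None of these inputs is in the protocol. Assume half of women are interested in the information. Let t1 and t0 be the pick-up rates of interested and other women, h1 and h0 their shares rating the pamphlet helpful, and c the share of non-takers given it on admission. Assume that a woman's rating does not depend on when she received it.

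- Takers: (t1·h1 + t0·h0)/(t1 + t0)
- Non-takers: [(1 − t1)h1 + (1 − t0)h0]/(2 − t1 − t0)
- Surveyed sample: (w1·h1 + w0·h0)/(w1 + w0), where wi = 0.5[ti + (1 − ti)c]
- All women: 0.5·h1 + 0.5·h0 = 75% in every row below

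| t1, t0 | h1, h0 | Takers | Non-takers | Excess in surveyed sample, in points, at c = 0 / 0.5 / 0.9 / 1 |
|---|---|---|---|---|
| 0.6, 0.4 | 0.8, 0.7 | 76% | 74% | 1 / 0.3 / 0.1 / 0 |
| 0.6, 0.4 | 0.9, 0.6 | 78% | 72% | 3 / 1 / 0.2 / 0 |
| 0.8, 0.2 | 0.8, 0.7 | 78% | 72% | 3 / 1 / 0.2 / 0 |
| 0.8, 0.2 | 0.9, 0.6 | 84% | 66% | 9 / 3 / 0.5 / 0 |

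Worked for the last row: takers (0.8×0.9 + 0.2×0.6)/1 = 0.84; non-takers (0.2×0.9 + 0.8×0.6)/1 = 0.66. At c = 0.5, w1 = 0.45 and w0 = 0.30, giving (0.405 + 0.180)/0.75 = 0.78, which is 3 points above 0.75.

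Takers exceed the population by 1 to 9 points and non-takers by 2 to 18. The overall figure is unaffected at c = 1, which is what Sections 3 and 3.1 describe. If interested women gained less from the pamphlet (h1 below h0), every sign would reverse. For scale, the 95% half-width at 75% with 100 surveys is 1.96×√(0.75×0.25/100) = 8.5 points.

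**The case against.** **The stronger reading.** A reader might infer that pick-up by motivated women inflates the reported helpfulness. Suppose, as an assumption, that 40% take the pamphlet, 85% of them would call it helpful, and 55% of the others would. One might then say the survey shows 85% where universal distribution would give 67%, an 18-point overstatement (85% against 73%, or 12 points, at 60% pick-up). The documents do not support this. It needs a survey made up only of takers, whereas non-takers are to receive the pamphlet on admission and are eligible on that basis. With complete admission provision the same inputs give 0.4×85% + 0.6×55% = 67% for the whole sample, with no overstatement by this route. Nor does any text fix the direction: women who seek information may already be well informed and gain less. This objection stands in full.

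**The text can be read more kindly.** Section 3.4 covers clinic and labor unit together and may mean only that everyone gets the same content. That softens the conflict with 3.4. It does not remove the conflict between 3.5.3 and the statement in Section 3 that material is dispensed at clinic visits.

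**Exposure may already be captured.** The questionnaire is not shown, and criterion 3 requires receipt to be established somehow. That is fair, and the fix is conditional on it. But criterion 3 is met by either route, so checking it need not show which one applied.

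**Waiting-room availability is a legitimate, pragmatic way to deliver material.** It is. The protocol should then say so and limit its conclusion. No comparison by exposure is planned, so confounding of such a contrast is a caution for reporting and not a fault in a stated analysis.

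**Conclusion.** The inconsistency is real. Sections 3 and 3.4 present antenatal delivery as general, while Section 3.5.3 makes it partly voluntary and admits incomplete staff contact. Combined with the either-or eligibility criterion, this leaves the antenatally exposed share of the 100 respondents unknown and self-selected. Ratings cannot then be attributed to the antenatal-plus-repeated education in the aim. Because the survey is anonymous and unlinked, the gap cannot be filled afterwards.

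The size cannot be stated from the protocol, which gives no pick-up rate, rating or admission coverage. On the assumed inputs above, the overall excess ranges from 0 with complete admission provision to 9 points with none. Neither a general inflation of the results nor a particular number of points can be claimed. The conclusion assumes that the questionnaire does not already record the source and timing of receipt.

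**What to change.** 1. Reconcile Sections 3, 3.4 and 3.5.3. Either have the pamphlet handed to each eligible woman at an existing clinic check-in, with the waiting-room copies as a supplement, or state plainly that antenatal exposure is by voluntary pick-up.
2. In either case, unless the questionnaire already does so, add two tick items: where and how the pamphlet was received (clinic, labor or both; handed over or picked up), and whether it was read before labor.
3. Report the share of respondents exposed antenatally, and describe results by exposure as a non-randomised contrast.
4. Limit conclusions about antenatal education to women who received and read the material before labor.

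The cost is a wording change and two short items on an anonymous form, with no new identifiers. A hand-out would add a small burden on clinic staff and some extra printed copies; correcting the wording alone avoids that burden but narrows what the study can claim.
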